### 3.7 Research Quality Assessment

We will employ several strategies used in our effectiveness trials to ensure fidelity and monitor “intervention drift” among providers delivering SHIM including: 1) *Training of providers*: We will provide a clinical competency training on HCV management followed by a knowledge assessment before starting twice-monthly ECHO; 2) *Clinic Site visits*: After creating a site matrix (number of OAT patients, clinicians, administrators, other services provided, hours, proximity of nearest psychiatric clinic, etc), our Project Coordinator will schedule site visits baseline and every 6 months to meet with clinicians and administrators at each site to discuss challenges and their experiences in delivering SHIM and assess quality and fidelity of implementing the intervention. We will use methods used in our Ukraine integration pilot study where we assessed organizational factors based on what's working, not working and goals for improvement [44]; 3) *Technical Assistance*: Clinic providers will be able to access technical assistance bi-weekly from ECHO and from our experts in between sessions using tele-consult, which will be monitored and assessed; 4) *Regular review of process measure data*: Rapid collection of process measures via our electronic data management system with real-time input will allow us to monitor implementation of the intervention and assess many primary, secondary and process outcomes.

## 4 Safety Monitoring and Adverse Event Reporting

### 4.1 Safety Monitoring

Close cooperation between the Investigators, clinical and research teams will be necessary in order to monitor participant safety and to respond to occurrences of toxicity in a timely manner. The team will have regularly scheduled conference calls during the period of study implementation, and additional ad hoc calls will be convened if required.

The study site Coordinators are responsible for continuous close monitoring and management of AEs. Sites are required to follow the detailed SOPs describing methods for AE reporting and toxicity management to ensure that AEs are reported and managed in accordance with the protocol and for alerting the Principal Investigator if unexpected concerns arise.

A sub-group of the Protocol Team, including the Principal Investigator, Clinical Consultant, and Co-Investigators will serve as Study Monitoring Committee (SMC). The SMC provides support to site clinicians regarding individual participant clinical management (toxicity management, clinical holds of study drug, study drug re-challenge, permanent discontinuations, etc.). The Site Coordinators will prepare routine study conduct and safety reports for the SMC, which will meet by conference call approximately monthly and will review safety data during a closed meeting. More frequent or ad hoc reviews of safety reports may be conducted by the SMC as needed. A recommendation to stop the trial may be made by the SMC at any such time that the team agrees an unacceptable type and/or frequency of AEs has been observed. If at any time a decision is made

to discontinue the study product in all participants, the PI will notify the Site Coordinators and the responsible IRB expeditiously.

### 4.2 Adverse Event (AE) Reporting

Adverse events (AE) are defined as any untoward medical occurrence experienced by participants during the study, and may or may not have a causal relationship with the treatment. Information regarding all AEs regardless of seriousness or severity will be recorded in the participant's source files. Grade 3 and higher adverse events and all creatinine AEs will be recorded on study forms. All SAEs must be reported on AE Log form. All AEs that result in a clinical hold or permanent discontinuation of study product are reported on AE Log form regardless of grade. Grade 3 and higher clinical AEs will be referred to a study clinician at the time of the visit.

All critical laboratory values will be reported as applicable per site SOPs. Participants who are not present at the study site at the time a laboratory AE requiring retesting or follow-up is identified will be followed as deemed clinically appropriate. With appropriate permission of the participant, and whenever possible, records from non-study medical providers related to untoward medical occurrences will be requested and required data elements will be recorded on study forms and/or in the participant's medical chart. All AEs regardless of severity will be followed clinically, until the AE resolves or stabilizes as per the appropriate toxicity algorithm. AEs will be assessed for all participants, regardless if they continue DAA or not, after enrollment through the final study visit.

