## 3 Study Design and Research Methods

### 3.1 Study conditions

#### 3.1.1 Standard of care (SOC)

As of today, HCV diagnostics and treatment is available through the network of specialized infectious diseases clinics. Other clinics (primary care, secondary level or clinics with other specialization) may prescribe and in some cases perform HCV screening, and in case of positive test result provide referrals to the specialized infectious diseases clinics or departments (hepatology centers). Upon admission, physicians are prescribing diagnostic tests to confirm the diagnosis, determine fibrosis stage, and detect possible contraindications. Based on the diagnosis and availability of medications, a treatment regimen is prescribed. Despite the fact that current MoH policy is permitting the use of international clinical guidelines, such as WHO or EASL, in routine practice the number and choice of diagnostic tests and treatment regimens is left to physician's discretion. In most cases, patients are required to have blood biochemistry (liver enzymes), quantitative HCV RNA, genotyping, liver ultrasound, FibroScan, kidney function tests. The cost of diagnostic tests is fully paid by the patients. The choice of treatment regimens usually includes the generic SOF formulations procured by the MoH or regional programs (see Rationale), or other DAA generics that recently became available for purchase at pharmacies. Hepatology center physicians are also prescribing follow-up tests (HCV RNA) to monitor treatment effectiveness.

In this study, the OAT clinics in the SOC arm will be informed of availability of medications at the hepatology centers and instructed to refer patients for screening (to primary care or other clinics, or harm reduction programs) and treatment (to hepatology centers).

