#### (3) simple, once-daily, pan-genotypic HCV treatment regimens

According to the prospective SHIM algorithm, certain conditions (e.g. decreased kidney function, cirrhosis) will trigger a referral to the hepatology center for specialist treatment. In other cases, the OAT physicians will be trained to prescribe the available DAA medications and provide adherence counseling. Given that the OAT patients show up at the clinics daily or on a regular basis, treatment will start as soon as the pre-treatment evaluation is complete. **Given the implementation science premise of this proposal, we will not control which regimens are prescribed by physicians.** On the individual level, the frequency of dispensing may vary depending on the patient's OAT clinic visit schedule, but should not be more frequent than once a week. HIV co-infection (present in almost half of the OAT patients) will be considered an indication for referral to an HIV clinic, but not the hepatology center. HCV treatment in HIV/HCV co-infected patients will be managed by the OAT physician in consultation with the HIV specialist.

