### 3.5.6 Data collection

Given the primary and secondary outcomes of interest, data collection for Aim 1 will include three main sources: clinical chart review data and quantitative survey of patients.

**De-identified medical chart review** data extracted by authorized clinic staff will inform outcomes P1-P3, S1a-d and S3b. We will use the electronic Simple Treatment Monitoring Application (STMA)

developed and used in our previous [35] and ongoing projects to collect detailed data on all relevant assessments and treatments, including HCV diagnostic tests, pre-treatment assessments, DAA treatment prescription, on-treatment and post-treatment monitoring, OAT admission and discharge, OAT medication prescription. The database will also collect information on important clinical covariates, including HIV, TB and HBV co-infection, mental health screening and its results, prescription of ART and other medications and side effects. STMA data will be collected on a monthly basis from all sites.

It is expected that physicians at the SHIM sites will comprehensively manage HCV care, and the medical charts and STMA will contain all up-to-date diagnostics and treatment information. However, all SOC sites' patients and possibly some SHIM patients will receive HCV services elsewhere, and their HCV-related clinical data will not be available at the OAT clinic. To ensure completeness of the key outcome data for all participants, we will use an external clinical data verification procedure, similar to one used in our ongoing IMPACT project. In order to avoid intervention contamination, this procedure is conducted by research staff, and not by OAT clinic personnel. At the end of each quarterly clinical data collection cycle, the data manager will generate the HCV treatment cascade report in STMA. For each patient who will not have information about any of the three primary clinical endpoints (HCV diagnosis, treatment initiation, post-treatment HCV RNA PCR) in the report, the interviewers will conduct a brief follow-up by phone. If the patient will report receiving this service, the interviewer will ask about when and where the service was received. At the second stage, the interviewers will contact the respective healthcare facilities to verify the receipt of the services and results (for assessments). This procedure will be enabled by a separate third-party disclosure agreement signed by the patient.

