For the secondary outcomes S2b-c, we will collect data using a **paper-based adherence form** administered by clinical personnel during patient visits at treatment initiation, medication pick-up at 4 and 8 weeks, and treatment completion at 12 weeks after initiation. The baseline form will assess self-efficacy and anticipated barriers to treatment adherence for the whole treatment period. The follow-up forms will assess treatment satisfaction, past 30-day and 7-day adherence using visual analog scale [36], side effects, reasons for non-adherence, and reasons for treatment discontinuation (if occurred). At treatment completion, the form will additionally assess the readiness and anticipated barriers to SVR check at 12 weeks after.

For the secondary outcomes S2a and S3a and relevant co-variables, we will collect data using a **patient survey**. The survey will be conducted for the pilot patients and all 3 arms of the main phase at baseline, treatment completion (or 12 weeks after initiation if not completed or 16 weeks after the baseline if not started) and 12 weeks after treatment completion (or 24 weeks after treatment initiation if not completed, or 28 weeks after the baseline if not initiated treatment).

The baseline survey will be administered after confirmation of the diagnosis using HCV RNA test. Patients who will test negative for HCV RNA will be excluded from the following study procedures.

All patient surveys will be collected by an independent interviewer, using study ID via UIPHP REDCap server with clerical checking and patient safeguards described in detail in the human subjects section.

The surveys will include demographics, geospatial assessment, depression (PHQ-9), substance use, alcohol use disorders (AUDIT-C), HIV comorbidity and treatment history, Chronic Liver Disease Questionnaire-Hepatitis C Version (CLDQ-HCV) [37], trust in physician scale [38, 39], HIV risk behaviors, family and social support [40], drug use and mental illness stigma [41], and socio-demographic information.

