### 4.4 Reporting Requirements for this Study

The Serious Adverse Event (SAE) Reporting Category, as defined in Version 2.0 (or latest version) of the DAIDS EAE manual, will be used for this study. The study agents for the purposes of SAE reporting are part of a fixed dose combination tablet: sofosbuvir/daclatasvir or sofosbuvir/velpatasvir.

The SAE reporting period for this study is per the DAIDS EAE manual and continues from enrollment of a trial participant to the end of trial follow-up for that participant. All reportable SAEs occurring during the study reporting period will be reported to the principal investigator in an expedited manner, within three reporting days of site awareness of the events (see definition in Appendix D of the DAIDS EAE Manual).

Reporting requirements for the local IRB will also be followed.

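### Adverse events are to be assessed in every participant, but no active collection route is the same in all three arms, so ascertainment is likely to differ by arm

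*Combined protocol and SAP*

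**What the plan says.** Section 4.2 sets the commitment: "AEs will be assessed for all participants, regardless if they continue DAA or not, after enrollment through the final study visit". It also asks for records from outside providers about untoward events, subject to the participant's permission and to feasibility. Section 4.1 makes site coordinators responsible for continuous monitoring and refers to SOPs for the reporting method.

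The data-collection sections name these sources:

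- **SHIM visits.** Section 3.1.2, item (4), includes a side-effect assessment at 4, 8 and 12 weeks of treatment.
- **Adherence form.** Section 3.5.6 describes a paper form that clinical staff fill in when treatment starts, at the two later pick-ups (weeks 4 and 8), and when the course ends at week 12. "The follow-up forms will assess treatment satisfaction, past 30-day and 7-day adherence using visual analog scale [36], side effects", among other items.
- **STMA.** Section 3.5.6 includes side effects in this chart-review database, collected monthly from all sites. The same section expects that all patients at SOC sites and "possibly some SHIM patients will receive HCV services elsewhere, and their HCV-related clinical data will not be available at the OAT clinic".
- **External verification.** Research staff telephone a patient, and then the treating facility, when information is missing on any of the "three primary clinical endpoints (HCV diagnosis, treatment initiation, post-treatment HCV RNA PCR").
- **Patient survey.** It is given in all three arms, with substitute times for participants who do not start or complete treatment. The listed topics include no adverse-event item, and the schedule table in Section 3.5.6 has no adverse-event row.

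Two further statements bear on coverage. Under SHIM, "certain conditions (e.g. decreased kidney function, cirrhosis) will trigger a referral to the hepatology center" (Section 3.1.2, item 3). Section 4.4 describes the study agents for SAE reporting as "part of a fixed dose combination tablet: sofosbuvir/daclatasvir or sofosbuvir/velpatasvir". Sections 3.1.2 and 3.2 say that the study does not control regimens, and Section 3.1.1 lets SOC physicians choose publicly procured generics "or other DAA generics that recently became available for purchase at pharmacies".

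**The concern.** The plan recognises that data from care given elsewhere will not reach the OAT clinic, and it builds a verification procedure for the cascade outcomes. It builds nothing equivalent for adverse events. Whether an event is recorded may then depend on where the participant is treated, and place of treatment is what randomisation changes.

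The groups least well reached are SOC patients treated at hepatology centres, SHIM patients referred out, and participants in any arm who never start treatment. The referred SHIM patients are selected on conditions such as cirrhosis or reduced kidney function, so they differ clinically from those kept on site.

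Under Section 4.1 the study monitoring committee may recommend stopping if the kind or number of adverse events is judged unacceptable. A frequency is hard to interpret when the chance of recording an event differs between arms. The same holds for any table of events by arm in the final report.

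**Working it through.** The plan gives no adverse-event rate, safety power or capture rate, so there is no figure to reproduce. The check sets each route against each group of participants.

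| Route | SHIM, treated on site | SHIM, referred out | SOC, treated elsewhere | Never treated |
|---|---|---|---|---|
| Side-effect check, weeks 4, 8, 12 (3.1.2) | yes | not stated | no stated equivalent | no |
| Adherence form (3.5.6) | yes | who completes it is not stated | who completes it is not stated | no pick-up, so no form |
| STMA from OAT charts (3.5.6) | yes | HCV-related data may be absent | HCV-related data expected to be absent | chart entries only |
| External verification (3.5.6) | not for AEs | not for AEs | not for AEs | not for AEs |
| Patient survey (3.5.6) | given; no AE topic listed | same | same | same |
| Outside records (4.2) | once an event is known | same | same | same |

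Only the first column has a clear active route. The survey is the one contact specified for all four columns.

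**Illustration of unequal capture.** From the plan: 160 participants per arm (4 clinics × 40). Assumed: equal true risk *p* in both arms, average capture of 90% in a SHIM arm, and capture *c* of 60% or 30% in SOC.

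Expected recorded events = 160 × *p* × capture. Apparent ratio, SHIM to SOC = 0.90 / *c*.

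- *p* = 5%: SHIM 160 × 0.05 × 0.90 = 7.2. SOC 160 × 0.05 × 0.60 = 4.8, or 160 × 0.05 × 0.30 = 2.4.
- *p* = 2%: SHIM 160 × 0.02 × 0.90 = 2.9. SOC 160 × 0.02 × 0.60 = 1.9, or 160 × 0.02 × 0.30 = 1.0.
- Ratio: 0.90 / 0.60 = 1.5, or 0.90 / 0.30 = 3. With equal capture it is 1.
- Chance that SOC records no event at *p* = 2% and *c* = 30%: (1 − 0.02 × 0.30)^160 = 0.994^160 = 0.38.

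**Illustration of referral within SHIM.** Assume a share *r* of SHIM patients is referred out, with *k* times the risk of the others. The share of true SHIM events arising outside the OAT clinic is *rk* / (1 − *r* + *rk*).

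- *r* = 10%, *k* = 1: 0.10 / 1.00 = 10%.
- *r* = 20%, *k* = 2: 0.40 / 1.20 = 33%.
- *r* = 30%, *k* = 3: 0.90 / 1.60 = 56%.

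The two illustrations are separate, since the first uses one average capture rate for the SHIM arm. They also pull in different directions. Closer observation makes SHIM look worse than SOC, while missed events in referred patients make SHIM look better than it is.

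**The case against.** The case against has several parts, and much of it stands.

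- **Other sources exist.** A reader might infer that the form at OAT dispensing visits is the only structured capture. It is not: STMA has a side-effect field for all sites, and Section 4.1 adds coordinators and SOPs. The SOPs and the survey instrument are not in the documents and may close part of the gap. The form's text names clinical personnel but neither a clinic nor an arm. Adherence and satisfaction are secondary outcomes to be compared across arms, which suggests that the form is meant for all three. What is missing is a statement of who completes it away from the OAT clinic.
- **Adverse events are wider than HCV care.** Section 3.5.6 says that HCV-related data will be absent, not all clinical data. OAT patients attend regularly, so clinic staff may learn of a hospital admission. A claim that SOC will have almost no safety data is therefore unsupported. Hearing of events in this way is still passive.
- **Safety is not a formal comparison.** It is not an endpoint or a hypothesis, and Section 3.5.8 plans no test between arms. This limits the consequence to committee review and descriptive reporting.
- **Follow-up length.** A reader might set 28 weeks for an untreated participant against 12 + 52 = 64 weeks for one tested for re-infection. The schedule does not support this. It ends 12 weeks after completion, which for a 12-week course is 12 + 12 = 24 weeks after initiation, against 28 weeks after baseline if untreated. The 12-month test is only recommended and has no column. What stands is that Section 4.2 does not define the final visit.
- **Study agents.** Section 4.4 need not mean that SAEs on other regimens go unrecorded. Sections 4.2 and 4.3 put all SAEs on the AE Log, and Section 4.3.2 judges relatedness to DAAs in general. The inconsistency of wording remains.

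**Conclusion.** The concern holds in a limited form. The commitment in Section 4.2 has no stated active collection route that is common to the three arms. Capture outside the OAT clinic and in untreated participants is largely passive as written. Ascertainment is therefore likely to differ by arm and, within SHIM, by clinical condition.

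The size is unknown. The 1.5- to 3-fold range and the 10% to 56% range rest entirely on assumed risks, capture rates and referral shares. A reader might go further and say that SOC and referred patients will look falsely safe, or attach a fixed ratio such as 4-fold. The documents support a likely imbalance but neither that certainty nor any particular ratio.

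The point does not touch the primary cascade outcomes. It should be corrected because event frequency can lead to a recommendation to stop, and because the correction uses contacts that already exist.

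**What to change.** 1. Add a short standard block on adverse events, hospitalisation and DAA discontinuation to the patient survey at treatment completion and 12 weeks later, or at the substitute times in Section 3.5.6, in all three arms. Add a matching row to the schedule table.
2. Do not rely on the quarterly calls. They reach only patients who lack a cascade endpoint, so adverse-event questions there would create a new imbalance.
3. Where participants consent, extend third-party verification to reported hospitalisations and deaths.
4. State in Section 4.2 how, when and by whom events are collected for participants treated elsewhere or never treated. State also who completes the adherence form when medication is dispensed away from the OAT clinic.
5. Define the adverse-event window. Report events by arm over a common window from enrollment, with referred-out patients shown separately.
6. Reconcile the study agents named in Section 4.4 with Sections 3.1.1, 3.1.2 and 3.2, under which other DAA regimens may be used.

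The cost is slightly longer interviews, more events to record, and possibly IRB review of a revised survey and disclosure agreement. No new visits are needed.

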### 4.3 Serious Adverse Events

Serious adverse events (SAEs) will be defined per CFR 312.32 guidelines, as AEs occurring at any dose that:

- Result in death;
- Are life-threatening adverse events;
- Require inpatient hospitalization or prolongation of existing hospitalization;
- Result in persistent or significant disability/incapacity; or
- Are congenital anomalies/birth defects.

Important medical events that may not result in death, be life-threatening, or require hospitalization may be considered serious when, based upon appropriate medical judgment, they may jeopardize the participant or require medical or surgical intervention to prevent one of the outcomes listed above.

Note: All SAEs must be reported on the AE Log.

#### 4.3.1 Grading System

All AEs will be graded using the DAIDS AE Grading Table, Version 1.0, December 2004 (Clarification dated August 2009) and the DAIDS Addendum 2 - Male Genital Grading Table, which are available at <http://rsc.tech-res.com/safetyandpharmacovigilance/>. Grade 1 creatinine toxicity will be determined by either the DAIDS AE Grading Table OR Grade 1 as defined by creatinine > 1.5x the participant's baseline serum creatinine, whichever is higher."

